#### Design

Sixty men living with obesity will be recruited and randomly assigned to either a standard care group (N = 30) or an intervention group (N = 30). Eligible participants will be age 19 years or older, living with obesity (BF  $\ge$  28%), able to perform exercises, but not currently engaged in regular physical activities (150 min of moderate to vigorous aerobic activities + two sessions of RT per week). Participants will be asked to maintain their current dietary habits within the duration of the project.

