#### Statistical analysis

Sample size calculations was done based on the anticipated change in the proportion of obese men to achieve the PA guidelines (minimum of 150 minutes spent at MVPA in a week in addition to two sessions of RT). It is predicted that the proportion of men living with obesity who meet physical activity guidelines (both aerobic MVPA and RT) in the RT+ group will increase to 26.2% (similar to lean counterparts) at follow-up compared with 0% increased for the control group. The alpha level and power of analysis were set at 0.05 and 80% respectively, considering a drop-out rate of 30% in each group. A total of 23 people per group were required, so we will recruit 30 per group.

To evaluate the effect of the intervention on the main outcome (% of people reaching the PA guidelines 36 weeks after the intervention), a logistic regression model will be used. The independent variables will include age, PA level at baseline, the randomized group, and other potential confounding variables.

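### The primary logistic model is committed to further confounders beyond group, age and baseline activity, although the plan's own rates imply only about 6 responders

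*Protocol*

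**What the plan says.** The Design section of the protocol randomises 60 men, 30 to each arm, and excludes men who already meet the activity guidelines. The Statistical analysis section makes the main outcome binary (meeting the guidelines 36 weeks after the intervention) and analyses it by logistic regression. On the terms of that model it says: "The independent variables will include age, PA level at baseline, the randomized group, and other potential confounding variables". It gives no number or list for the last group of terms, and it does not say whether the group effect is tested by a Wald, likelihood-ratio, penalised or exact method.

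For sample size, the same section assumes that the proportion meeting the guidelines "in the RT+ group will increase to 26.2% (similar to lean counterparts) at follow-up compared with 0% increased for the control group". It adds: "The alpha level and power of analysis were set at 0.05 and 80% respectively". It requires 23 men per group and recruits 30, "considering a drop-out rate of 30% in each group".

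**The concern.** Randomisation removes systematic confounding of the group effect. Covariates in the primary model then have one useful purpose, which is to explain outcome variation, and a general wish to control for confounders is not a reason to add them. With a binary outcome and very few responders, added terms are not free. They use up the little information there is, and the usual large-sample reference distribution fits worse with each one.

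The sample size comes from an unadjusted comparison of two proportions, so it allows nothing for covariates. The Method section collects many candidates at baseline (weight, waist, body composition, fitness, lipids, glucose, blood pressure and questionnaire scales), so several extra terms are realistic. At stake is the one test on which the trial's conclusion rests: its power or its false-positive rate, depending on the test used.

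**Working it through.** **Inputs from the protocol.** RT+ rate 0.262. Control rate 0, since the assumed increase is zero and men already meeting the guidelines are not eligible. Alpha 0.05, taken as two-sided because sidedness is not stated. Power 80%. 23 per group required, 30 recruited, 30% dropout.

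**The plan's own figure.** The unpooled two-proportion formula gives

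n = (1.960 + 0.842)² x (0.262 x 0.738 + 0 x 1) / 0.262² = 22.1, rounded up to 23.

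This matches the protocol, and no covariate enters it. Recruitment of 30 matches 23 x 1.3 = 29.9. If 30% of 30 drop out, 30 x 0.7 = 21 per arm remain, so both 23 and 21 are used below.

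**Expected responders.** 0.262 x 23 = 6.03; 0.262 x 21 = 5.50; 0.262 x 30 = 7.86 if nobody drops out. All are in the RT+ arm. Group, age and baseline activity use three slopes: 6.03 / 3 = 2.0 responders per slope.

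**Effect of further terms.** Logistic models were simulated with group plus independent standard-normal covariates unrelated to outcome. (In one set of runs baseline activity was given a log-odds of 0.7 per SD; power was nearly the same at 0.) Power uses 26.2% v 0%. Type I error uses (0.262 + 0) / 2 = 13.1% in both arms, which keeps the expected count at 46 x 0.131 = 6.03. Likelihood-ratio statistics are compared with 3.841. Ranges cover separate simulations of 500 to 4000 runs per cell. At a power of 80% the Monte Carlo standard error, √(0.8 x 0.2 / N), is 1.8 points for N = 500 and 0.6 for N = 4000.

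| Covariates beyond age and baseline activity | Slopes | Responders per slope (of 6.03) | Firth power, 23 per arm | Firth power, 21 per arm | ML likelihood-ratio type I error, 23 per arm |
|---|---|---|---|---|---|
| 0 | 3 | 2.0 | 80-83% | 75-76% | about 8-9% |
| 2 | 5 | 1.2 | 75-77% | 70-72% | 10-11% |
| 4 | 7 | 0.86 | 70-72% | 63-64% | 12-13% |
| 6 | 9 | 0.67 | 62-65% | 53-56% | 13-15% |

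Firth type I error stayed at or below 5% throughout (4.1% with the two named covariates at 23 per arm).

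**Wald test under maximum likelihood.** With no control responders the group coefficient has no finite estimate (separation). Wald power is about 0% and its type I error about 1-2%, whatever the number of covariates.

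**A covariate that does predict outcome.** A strong one (assumed odds ratio about 3 per SD) was added to group and two noise terms. Firth power went from 81% to 80% at the planned 0% control rate, and from 60% to 63% at an assumed 3% control rate.

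**The case against.** The strongest objection is that naming and limiting covariates is ordinary SAP content, and the SAP is not shown. That would answer a complaint that the terms are unnamed. It does not answer this one: the protocol already commits the primary model to terms beyond the three it names, and a SAP that faithfully lists four or six would still carry the losses in the table. It is fair, though, that the text sets no number. One or two extra terms would satisfy it, and at 23 per arm two extra noise terms leave Firth power only 3 to 5 points below the 80% target.

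A second objection is that each harm belongs to a test the protocol does not name. This stands, and it limits the claim. A reader might infer that ordinary maximum likelihood inflates the false-positive rate in general. It does so for the likelihood-ratio test; the Wald test, which is common software output, is conservative. Nor does likelihood-ratio power collapse: it was 92-95% with the two named covariates and 77-89% with eight in total, although with an inflated error rate. For the Wald test, separation has already removed the power and extra terms are irrelevant.

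Two other stronger readings also go too far. One is that every added term costs power: a strongly prognostic covariate need not. The other is that covariates will be chosen after looking at the data, or taken from visits after randomisation. Picking the best of five covariate sets would raise likelihood-ratio type I error from 8.9% to 14.1% in simulation, but the protocol describes no such procedure, and its activity covariate is explicitly the baseline one. These are reasons to write a tight rule, not defects in the text.

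**Conclusion.** The point holds as a badly fixed rule for the primary model, and it should be changed. Adding unspecified confounders to a randomised comparison with about 6 expected responders (5.5 at 21 per arm) serves no purpose that randomisation has not already served.

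At 23 per arm, six non-prognostic additions cost roughly 15 to 21 points of Firth power (80-83% down to 62-65%), or bring likelihood-ratio type I error to nearly three times nominal, from a level already well above 5%. A Wald test is unusable with or without them. The size of the harm therefore cannot be fixed until the test is named.

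These figures rest on the plan's rates of 26.2% and 0%, a two-sided 0.05 level, and covariates that are independent of each other and of outcome. Prognostic covariates would cost less, and fewer additions would do less harm.

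**What to change.** In the protocol's Statistical analysis section:

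1. Delete the closing clause of the sentence on independent variables, which adds further confounders. Fix the primary model as randomised group, age and baseline activity, all measured before randomisation, with no data-driven selection.
2. Name the test of the group effect: a Firth penalised likelihood-ratio test, or an exact test. Closing the list alone is not enough, because the three-term model still has about 8-9% type I error with the ordinary likelihood-ratio test and almost no power with the Wald test.
3. Put any further baseline covariate in one labelled sensitivity analysis that cannot replace the primary result.

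The cost is a sentence or two, with no change to data collection. The downside is that a chance imbalance in another baseline factor is handled only in the sensitivity analysis. The closed Firth model keeps about the planned 80% power at 23 per arm, but only 75-76% if dropout leaves 21. An unadjusted Fisher exact test would have about 76% and 68% respectively, so the choice between the two should be made knowingly.
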